Data in relation to carriage in Australia are scant and very little is known about overall carriage prevalence of *Neisseria meningitidis* (i.e. all strains), or the proportion of strains that are meningococcal serogroup B. The only Australian data available in the literature reporting 1.7% carriage were from a sample of 294 school aged children of various ages in Queensland and was conducted in 1989.(12) The improvement in sensitivity of newer molecular diagnostic techniques and the fact that South Australia regularly reports higher Invasive Meningococcal Disease rates than Queensland leads us to suspect that baseline carriage in South Australian adolescents will be higher than 1.7%. In carriage studies conducted in Europe, carriage prevalence was estimated at 4-5% in infants to a peak of 23-7% in 19-year olds. Recently presented carriage rates from Nottingham University in the UK ranged from 14.3% - 46.2% for all serogroups at the commencement of the university year and 6 months later.[Oldfield N et al. IPNC Mancester, UK, September 2016] Carriage rates for serogroup B ranged from 3.3% to 8.5% over the same time period. As no carriage data exist in Australia since commencement of the meningococcal C vaccine program, we will conduct a longitudinal pilot study of 500 first year university students during orientation week in 2017 at the University of Adelaide (Study Part 2). These students will undergo a posterior pharyngeal swab and complete a short questionnaire to collect information about possible risk factors at the beginning of university and then 3 months later.

Age is one the most important factors influencing carriage, with peak carriage occurring around 18- 19 years of age. Other factors that influence carriage are being male, concomitant respiratory infections, active and passive smoking, number and closeness of social contacts, and low socioeconomic status.(6) Disease is a rare outcome of infection (5) but the relationship between carriage and disease incidence is not fully understood. With carriage rates significantly higher in adolescents, a reduction in carriage in this group has the potential to provide protection to unvaccinated people (herd immunity), including infants.

Study Part 3: Cross-sectional carriage study

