6. STATISTICAL METHODS FOR GROUP COMPARISONS

Throughout this section the following details are provided for each outcome variable:

- Outcome: a description of the outcome variable.
- Effect: the measure of effect to be reported.
- Analysis: the type of statistical analysis to be performed.

For each outcome variable, statistical significance will be assessed at the 0.05 level using a two-sided superiority test. In addition to effect estimates and p-values, 95% confidence intervals will be reported to express uncertainty about the estimated effects.

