6.1 Vaccination Definition

School leavers who participated in the High School B Part of It RCT will be considered vaccinated if they have received two doses of Bexsero[®] at least one month prior to the date of the throat swab.

Vaccination will be confirmed in students who previously participated in the high school cluster randomised trial through the original study database. Participants who did not take part in the cluster randomised trial will be asked to provide consent to contact their immunisation provider to confirm vaccination history.

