6.2 Adjustment

Adjustment will be made for risk factors that had a two-tailed p-value < 0.05 in the multivariable model for baseline disease-causing carriage in the High School B Part of It RCT (see <https://clinicaltrials.gov/ct2/show/NCT03089086> for description of study). These include current cold or sore throat (no, yes), smoking cigarettes (no, yes), smoking water pipes (no, yes), days out at a pub/club in last week (0, 1 or more), people kissed in last week (0, 1 or more), and ethnicity (Caucasian, Asian, Aboriginal or Torres Strait Islander, Other). Adjustment will also be made for alcohol consumption in the last month (no, yes), as this emerged as an important risk factor

for disease-causing carriage in a preliminary analysis of 2018 School Leaver data. Previous vaccination with MenACWY (no, yes) and participation in the High School B Part of It RCT (no, yes) will also be considered for inclusion in the adjusted model. In order to address each hypothesis, both unadjusted and adjusted analyses will be performed, with primary conclusions to be based on the results of adjusted analyses. No adjustment will be made for risk factors in the analysis of carriage of genogroups A, C, W and X, as only small numbers of cases are expected to be detected.

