6.3 Multiple comparisons and multiplicity

No adjustment will be made for multiple comparisons, as there is only a single primary outcome and the multiple secondary outcomes are of less importance and will be considered exploratory.

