6.5 Secondary Outcomes

6.5.1 Carriage prevalence of all genogroups of *N. meningitidis* in school leavers in 2018 compared to 2019

Outcome: Binary outcome based on the presence of any *N. meningitidis*

(groupable or non-groupable) by PCR.

Effect: Odds ratio for all genogroups of *N. meningitidis* (2018 vs 2019).

Analysis: Test for a difference using logistic regression. Adjustment will be conducted as described in 6.2.

6.5.2 Carriage prevalence of each individual group of *N. meningitidis* (A, B, C, W, X, Y, and non-groupable) in school leavers in 2018 compared to 2019

Outcome: Binary outcomes (one for each group) based on the presence of specific meningococcal DNA by PCR for genogroups A, B, C, W, X, Y and non-groupable.

Effect: Odds ratio for *N. meningitidis* carriage for each genogroup (2018 vs 2019).

Analysis: Test for a difference using logistic regression. Adjustment will be conducted as described in 6.2.

6.5.3 Carriage prevalence of disease-causing genogroups of *N. meningitidis* (A, B, C, W, X, Y) in vaccinated compared to unvaccinated school leavers

Outcome: Binary outcome based on the presence of at least one disease-causing genogroup of *N. meningitidis* (A, B, C, W, X, Y) by polymerase chain reaction (PCR).

Effect: Odds ratio for disease-causing genogroups of *N. meningitidis* (4CMenB Vaccinated vs 4CMenB Unvaccinated).

Analysis: Test for a difference using logistic regression. Adjustment will be conducted as described in 6.2.

6.5.4 Carriage prevalence of all *N. meningitidis* in vaccinated compared to unvaccinated school leavers

Outcome: Binary outcome based on the presence of any *N. meningitidis* (groupable or non-groupable) by polymerase chain reaction (PCR).

Effect: Odds ratio for any *N. meningitidis* (4CMenB Vaccinated vs 4CMenB Unvaccinated).

Analysis: Test for a difference using logistic regression. Adjustment will be conducted as described in 6.2.

6.5.5 Carriage prevalence of each individual group of *N. meningitidis* (A, B, C, W, X, Y, and non-groupable) in vaccinated compared to unvaccinated school leavers

Outcome: Binary outcome (one for each group) based on the presence of *N. meningitidis* (groupable and non-groupable) by PCR.

Effect: Odds ratio for each individual genogroup of *N. meningitidis* (4CMenB Vaccinated vs 4CMenB Unvaccinated).

Analysis: Test for a difference using logistic regression. Adjustment will be conducted as described in 6.2.

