6.5.6 Carriage prevalence of disease-causing genogroups of *N. meningitidis* (A, B, C, W, X, Y) among vaccinated school leavers by timing of vaccination

Outcome: Binary outcome based on the presence of at least one disease-causing genogroup of *N. meningitidis* (A, B, C, W, X, Y) by polymerase chain reaction (PCR).

Effect: Odds ratio for disease-causing genogroups of *N. meningitidis* for each additional month since vaccination (based on receipt of the 2nd dose).

Analysis: Test for an association using logistic regression, with months since vaccination treated as a continuous variable. Adjustment will be conducted as described in 6.2.

6.5.7 Carriage prevalence of all genogroups of *N. meningitidis* among vaccinated school leavers by timing of vaccination

Outcome: Binary outcome based on the presence of any *N. meningitidis* (groupable or non-groupable) by polymerase chain reaction (PCR).

Effect: Odds ratio for any *N. meningitidis* for each additional month since vaccination (based on receipt of the 2nd dose).

Analysis: Test for an association using logistic regression, with months since vaccination treated as a continuous variable. Adjustment will be conducted as described in 6.2.

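### The vaccine-status and months-since-vaccination models (SAP 6.5.3–6.5.7) treat leavers as independent although vaccination came partly through a cluster randomised trial; standard errors clustered on year-12 school are a cheap safeguard

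*SAP*

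**What the plan says.** For vaccinated against unvaccinated leavers (SAP 6.5.3–6.5.5) the whole specification is "Analysis: Test for a difference using logistic regression. Adjustment will be conducted as described in 6.2". For months since the second dose (SAP 6.5.6–6.5.7) it is "Test for an association using logistic regression, with months since vaccination treated as a continuous variable", with the same adjustment. SAP 6.2 lists individual behaviours, symptoms and ethnicity. MenACWY vaccination and RCT participation are only to be considered, and school is not listed. No random effect, generalised estimating equation (GEE) or robust variance appears for Part 3.

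On where the exposure comes from, SAP 6.1 says "Vaccination will be confirmed in students who previously participated in the high school cluster randomised trial through the original study database". Protocol 4.1 invites former trial participants into Part 3. Protocol 5.3 has Group B year-12 students coming back later for their doses and sends invitations to year-12 students through their schools. Protocol 6.2.2 lists the name of the school among the questionnaire items.

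On what the results are for, SAP 6 says "95% confidence intervals will be reported to express uncertainty about the estimated effects", SAP 6.2 bases its reading on adjusted models, "with primary conclusions to be based on the results of adjusted analyses", and SAP 6.3 says "the multiple secondary outcomes are of less importance and will be considered exploratory".

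**The concern.** An ordinary logistic standard error assumes that, given the covariates, one leaver's carriage says nothing about another's. For a given exposure the error is understated only when two things hold together: the exposure is alike within a group, and so is the residual outcome.

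The first is plausible here. Part of the vaccination was allocated by cluster, and Group B was dosed later, so both status and months since dose 2 can follow the school. The documents provided do not state the unit of randomisation; school is assumed.

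The second is possible but not shown. Protocol 2.1 names "number and closeness of social contacts" as an influence on carriage, and classmates share contacts. Only the correlation left after the SAP 6.2 adjustment counts.

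If both hold, the intervals for vaccine effect and for waning are too short. Protocol 2.2 expects the vaccinated/unvaccinated comparison to inform vaccine funding decisions, so its stated precision deserves to be right even though the outcomes are exploratory.

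**Working it through.** **The plan's own figure.** SAP 5 gives 4,096 per year for 8.0% v 6.4%, 80% power, two-sided 0.05. The pooled two-proportion formula gives 4,096 and power 0.800. That figure concerns the year comparison. No sample size, power or ICC is stated for 6.5.3–6.5.7.

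**Inputs from the documents.** N = 2 × 4,096 = 8,192; carriage 8% (SAP 5); about two thirds vaccinated (Protocol 2.2).

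**Inputs assumed.**
- Leavers per school, m: 40 if school effects persist over both years, 20 if only same-year classmates share risk. With 205 schools, 8,192/205 ≈ 40.
- Residual carriage ICC: 0.005, 0.01 or 0.02.
- Within-school exposure correlation, r: 0.2–0.5. It is below 1 because non-RCT leavers (SAP 6.1), students who declined vaccination (Protocol 2.1) and later Group B vaccinees are included, and each school supplies two year-12 cohorts.

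**Formulas.** Design effect DE = 1 + (m − 1) × ICC × r; standard error multiplier = √DE; true alpha = 2[1 − Φ(1.96/√DE)].

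**Vaccine status, ICC 0.01**

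| m | r | DE | √DE | True alpha |
|---|---|---|---|---|
| 20 | 0.2 | 1 + 19×0.01×0.2 = 1.038 | 1.02 | 0.054 |
| 20 | 0.5 | 1 + 19×0.01×0.5 = 1.095 | 1.05 | 0.061 |
| 40 | 0.2 | 1 + 39×0.01×0.2 = 1.078 | 1.04 | 0.059 |
| 40 | 0.5 | 1 + 39×0.01×0.5 = 1.195 | 1.09 | 0.073 |

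Over the same grid, ICC 0.005 gives alpha 0.052–0.061, ICC 0.02 gives 0.059–0.096, and ICC 0 gives 0.050.

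**On the odds-ratio scale.** Under independence, with 5,461 vaccinated and 2,731 not, SE(log OR) = √[(1/5,461 + 1/2,731)/(0.08 × 0.92)] = 0.0864, so the interval around OR 1.0 is 0.844–1.185. At the top of the table (×1.09) it becomes 0.831–1.203.

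**Months since vaccination** (vaccinated only, so m ≈ 40 × 2/3 = 26.6 or 20 × 2/3 = 13.3; ICC 0.01, timing correlation 0.5). DE is 1.128 or 1.062, √DE 1.06 or 1.03, and alpha 0.065 or 0.057.

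**Simulation of the adjusted model.** 10,000 runs per row (Monte Carlo error about 0.002), 205 schools, no true effect. Covariates were cold, cigarettes, water pipe, pub/club, kissing, alcohol and ethnicity, with assumed prevalences and odds ratios. Residual ICC was 0.01 unless stated.

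| Setting | Rejection, ordinary | Rejection, clustered | True SE / model SE |
|---|---|---|---|
| m = 40, r = 0.2 | 0.054 | 0.048 | 1.02 |
| m = 40, r = 0.5 | 0.069 | 0.049 | 1.08 |
| School-year effects, m = 20, r = 0.5 | 0.060 | 0.050 | 1.05 |
| Delayed Group B (3% vaccinated in Group B 2018, 87% elsewhere) | 0.059 | 0.050 | 1.04 |
| Delayed Group B, residual ICC 0 | 0.050 | 0.052 | 1.00 |
| Months, m = 27, r = 0.5 | 0.059 | 0.049 | 1.04 |
| Months, m = 13, r = 0.5 | 0.055 | 0.053 | 1.02 |

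The simulated effects are equal to or slightly smaller than the formula's. Clustered errors restore the nominal level and cost nothing visible when the ICC is zero. Two limits: MenACWY and RCT participation are not in the simulated model, and schools have equal expected size.

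**The case against.** The strongest reply is that no error has been demonstrated. The documents do not show that carriage is correlated within school after adjustment. Swabs are taken from February to June after year 12, when leavers are at three universities, at work or attending clinics, so current contacts may follow those settings more than the former school. The models already adjust for kissing, pub visits, smoking and alcohol. A residual ICC near zero fits the documents as well as 0.01 does. This stands, and it is why the point is conditional.

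Second, the effect is small. In the delayed Group B setting the multiplier is 1.04, which moves the interval around OR 1.0 from 0.844–1.185 to 0.839–1.193. Sections 6.5.3–6.5.7 hold 1 + 1 + 7 + 1 + 1 = 11 tests; at alpha 0.059 the expected false positives, if every null is true, go from 0.55 to 0.65. This also stands. But the exploratory label in SAP 6.3 addresses multiplicity. It does not make an understated standard error correct.

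Third, the remedy has gaps. Clustered variance does not itself estimate an ICC. Leavers with no recorded school are still treated as independent. School is absent from the SAP 4.1 table, and the School Leaver Questionnaire (Version 5) cited in SAP 1 is not among the documents reviewed, so completeness of the school field is unknown. These points belong in the fix and do not remove the case for it.

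In the other direction, larger assumptions give larger effects: m = 80, carriage ICC 0.02 and exposure correlation 1.0 give DE = 1 + 79 × 0.02 × 1.0 = 2.58 and a standard error 61% larger. Complete exposure correlation conflicts with the mixed recruitment described above, so that figure is an outer bound only.

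**Conclusion.** The point holds as a cheap improvement to secondary analyses. The five model specifications ignore possible within-school correlation although part of the exposure came from a cluster randomised trial. At residual carriage ICC 0.01, the true standard error is about 2%–9% larger than the model reports and a nominal 5% test rejects about 5.4%–7.3% of the time (5.4%–6.9% in simulation). For months since vaccination the rejection rate is about 5.7%–6.5% by formula and 5.5%–5.9% by simulation. With ICC zero there is no effect.

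School as the randomised unit, leavers per school, ICC and exposure correlation are all assumed. Nothing is claimed about the primary 2018 v 2019 comparison or the 4,096 per year. Clustered errors correct precision only. They do not address confounding by school or by who chose vaccination.

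**What to change.** Add a short paragraph to the SAP covering 6.5.3–6.5.7:

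- Keep the planned logistic models and odds ratios, and compute cluster-robust standard errors with year-12 school as the cluster. Clustering on school, not school-year, covers correlation both within and across the two years.
- Treat each leaver of unknown school as a separate cluster, and report how many there are.
- Exempt genogroups A, C, W and X in 6.5.5. SAP 6.2 already drops adjustment for these, "as only small numbers of cases are expected to be detected", and robust variance is unreliable there for the same reason. Report counts with the planned unadjusted odds ratio, and state that independence is assumed.
- Report the school ICC for carriage, naming the method, since it needs a separate estimate. A value near zero would show that independence was harmless.

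The cost is this paragraph, cleaning and coding of school names, and one extra ICC estimate. On the Protocol 6.2.2 list no new data are needed; confirm that the questionnaire in use has the item and that it is well completed. The odds ratios do not change. Intervals would be about 2%–9% wider under the assumptions above.

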6.2 Adjustment

Adjustment will be made for risk factors that had a two-tailed p-value < 0.05 in the multivariable model for baseline disease-causing carriage in the High School B Part of It RCT (see <https://clinicaltrials.gov/ct2/show/NCT03089086> for description of study). These include current cold or sore throat (no, yes), smoking cigarettes (no, yes), smoking water pipes (no, yes), days out at a pub/club in last week (0, 1 or more), people kissed in last week (0, 1 or more), and ethnicity (Caucasian, Asian, Aboriginal or Torres Strait Islander, Other). Adjustment will also be made for alcohol consumption in the last month (no, yes), as this emerged as an important risk factor

for disease-causing carriage in a preliminary analysis of 2018 School Leaver data. Previous vaccination with MenACWY (no, yes) and participation in the High School B Part of It RCT (no, yes) will also be considered for inclusion in the adjusted model. In order to address each hypothesis, both unadjusted and adjusted analyses will be performed, with primary conclusions to be based on the results of adjusted analyses. No adjustment will be made for risk factors in the analysis of carriage of genogroups A, C, W and X, as only small numbers of cases are expected to be detected.

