9 STATISTICAL CONSIDERATIONS

9.1 DESCRIPTION OF STATISTICAL METHODS

9.1.1 GENERAL APPROACH

Logistic regression with adjustment for confouding will be used to identify factors associated with carriage and to compare carriage rates annually and between vaccinated and unvaccinated students. Changes in carriage between baseline and 3 months later will be evaluated using logistic regression with generalised estimating equations. In all analyses of carriage prevalence, effects will be described using odds ratios with 95% confidence intervals.

For comparing the difference in PCR +ve samples after freezing of the sample at 6 hours and 48 hours, we will compare paired proportions using a logistic model with generalised estimating equations, and assess agreement using a Kappa statistic.

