4. DESCRIPTIVE STATISTICS

4.1 Baseline characteristics

A descriptive comparison of the 2018 and 2019 groups will be conducted on the baseline characteristics presented in the following table.

Baseline characteristic	Categories
Age - years	-

Baseline characteristic	Categories
Sex	Female Male
Participation in the High School B Part of It Meningococcal Study	Yes No Unsure
Meningococcal B vaccine status	Yes (<= 12 months since dose 2) Yes (> 12 months since dose 2) Partial (only one dose) No
Meningococcal ACWY vaccine status	Yes (<= 12 months) Yes (> 12 months) No
Working status	Full time work Part time work Part time work + study Full time student Not working or studying Other
Smoking	Yes No
Cigarettes / day	-
Smoked e-cigarette in the last week	Yes No
Number of times smoked an e-cigarettes in the last week	-
Smoked water pipe in the last week	Yes No
Number of times smoked a water pipe in the last week	-
Number of persons/room	0 to 1

Baseline characteristic	Categories
	>1 to ≤2 >2
Ethnicity	Aboriginal Torres Strait Islander Caucasian Asian Middle East African Pacific Islander Other
Other smokers at home	Yes No
Antibiotics	None Stopped last month Stopped last week Yes, currently taking
Mouth wash used in the last month	Yes No
Times used mouth wash in last month	-
Number of days out in last week	-
Drank alcohol in the last month	Yes No
Number of days drank alcohol in last month	-
In those that drank in the last month, number of drinks on a typical drinking day	-
Days drank in the last month X typical drinking day	-
Number of people kissed in the last week	-
In current relationship	Yes No
Is partner a smoker	Yes

Baseline characteristic	Categories
	No N/A

Means and standard deviations will be reported for continuous variables, while frequencies and percentages will be reported for categorical variables.

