4.2 Working status categories

Mutually exclusive working categories grouped as described below:

- Full time work (full time work regardless of other categories)
- Part time work (working part time +/- gap year +/- looking for work)
- Part time work + study (working part time and studying at university of TAFE +/- looking for work)
- Full time study (exclusively TAFE or university student)
- Not working or studying (not working full time, part time, studying)
- Other
- Missing

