6.4 Primary Outcome

6.4.1 Carriage prevalence of disease causing genogroups of *N. meningitidis* (A, B, C, W, X, Y) in school leavers in 2018 compared to 2019

Outcome: Binary outcome based on the presence of at least one disease-causing genogroup of *N. meningitidis* (A, B, C, W, X, Y) by polymerase chain reaction (PCR).

Effect: Odds ratio for disease-causing genogroups of *N. meningitidis* (2018 vs 2019).

Analysis: Test for a difference using logistic regression. Adjustment will be conducted as described in 6.2.

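### The adjusted 2018-versus-2019 model has no swab-timing term and no table shows swab timing by year, although swabs run February to June and carriage may change in that window

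*SAP*

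**What the plan says.** SAP 6.4.1 defines the primary comparison and refers to 6.2 for covariates: "Analysis: Test for a difference using logistic regression. Adjustment will be conducted as described in 6.2". SAP 6.2 starts from risk factors in the high-school trial: "Adjustment will be made for risk factors that had a two-tailed p-value < 0.05 in the multivariable model for baseline disease-causing carriage". It names current cold or sore throat, cigarettes, water pipes, "days out at a pub/club in last week (0, 1 or more), people kissed in last week (0, 1 or more"), and ethnicity. It adds alcohol in the last month, and will consider MenACWY vaccination and trial participation. It ends with "primary conclusions to be based on the results of adjusted analyses". No swab date, week or month is named.

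SAP 4.1 states: "A descriptive comparison of the 2018 and 2019 groups will be conducted on the baseline characteristics presented in the following table". That table has no row for swab timing. The SAP uses swab date explicitly only in the vaccination definition (6.1), which requires two doses "at least one month prior to the date of the throat swab". No sensitivity analysis by timing appears.

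Protocol 9.1.1 makes a general commitment: "Logistic regression with adjustment for confouding will be used to identify factors associated with carriage and to compare carriage rates annually". It does not name swab date. Protocol 5.3 sets recruitment for February to June each year, and protocol 4.1 starts it in orientation week and continues until the target is met.

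**The concern.** Two independent cross-sections are compared, and each is collected over about five months. If carriage drifts within that window and the two years are swabbed at different points on average, the year coefficient mixes any programme effect with time of year.

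The protocol gives reason to expect drift. Section 2.1 cites a UK university where serogroup B carriage went from 3.3% at the start of the year to 8.5% six months later. Section 2.2 says carriage may change over three months from orientation week, and measuring that change is an objective of Study Part 2. Because recruitment runs until complete, the spread of swab dates depends on recruitment speed and not on a fixed schedule.

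The selection rule in SAP 6.2 is unlikely to supply the term. It draws on a baseline model fitted to students still at school, who could not show a start-of-university trend. The reference to confounding in protocol 9.1.1 does not fill the gap.

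At stake is the only primary comparison. A timing difference could create an apparent reduction or hide a real one, and the planned tables would not show whether the years were swabbed at similar times.

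**Working it through.** **1. The plan's own figure.** Inputs from SAP 5: 8% in 2018, 20% relative reduction (6.4% in 2019), 4,096 per year, two-sided alpha 0.05. A two-proportion test with pooled variance and no continuity correction needs 4,096 per year and has power 0.800. The sample size is correct. The target odds ratio, 2019 versus 2018, is (0.064/0.936)/(0.08/0.92) = 0.786. (The SAP reports 2018 versus 2019; I use the inverse throughout, so a reduction is below 1.)

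**2. An assumed slope.** The documents give no local slope, so I borrow the UK serogroup B figures in protocol 2.1, spread evenly over 26 weeks on the log-odds scale:

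[logit(0.085) − logit(0.033)]/26 = (−2.376 + 3.378)/26 = 0.0385 per week.

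I also use half and a quarter of this. Those can be read as a smaller true trend, or as existing covariates absorbing half or three quarters of it.

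**3. No true effect, 2019 swabbed earlier by d weeks on average.** Spurious odds ratio = exp(−slope × d). The apparent 2019 prevalence is put through the test in step 1. Example, half slope at 4 weeks: exp(−0.01926 × 4) = 0.926, so 2019 appears as 7.45% against 8%, and the test rejects 15.4% of the time.

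| Slope | Odds ratio, 2 wk | Odds ratio, 4 wk | Reject, 1 wk | 2 wk | 4 wk | 6 wk |
|---|---|---|---|---|---|---|
| Quarter | 0.981 | 0.962 | 5.2% | 5.6% | 7.6% | 10.8% |
| Half | 0.962 | 0.926 | 5.6% | 7.6% | 15.4% | 28.3% |
| Full | 0.926 | 0.857 | 7.6% | 15.4% | 44.8% | 77.0% |

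The full-slope row, with nothing absorbed, is an upper bound under this proxy.

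**4. True 20% reduction, 2019 swabbed later.** Power, from 80.0% with no difference:

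| Slope | 2 wk | 4 wk |
|---|---|---|
| Quarter | 73.5% | 66.0% |
| Half | 66.0% | 49.1% |
| Full | 49.1% | 18.0% |

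**5. Does a timing term repair it?** Logistic simulation, 1,000 runs per cell, with an assumed 21-week window and swab-date standard deviation of 4.7 weeks.

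| Scenario, no true effect | No term | Linear date | Month category |
|---|---|---|---|
| 2 wk, half slope | 0.098 | 0.059 | 0.057 |
| 4 wk, quarter | 0.088 | 0.050 | 0.046 |
| 4 wk, half | 0.154 | 0.048 | 0.049 |
| 4 wk, full | 0.470 | 0.047 | 0.045 |
| 6 wk, full | 0.796 | 0.043 | 0.046 |

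The 0.098 cell lies above the 0.076 of step 3 by about 2.6 Monte Carlo standard errors, √(0.076 × 0.924/1000) = 0.0084. I take it as simulation noise and rely on 0.076.

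If the whole 21-week rise instead falls in the first 7 weeks, the unadjusted rates are lower: 0.074 (4 wk, half), 0.223 (4 wk, full) and 0.440 (6 wk, full). With a date term they are 0.044 to 0.061.

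Power with a date term, linear trend, is about 77% at 2 weeks (half slope), 71% to 76% at 4 weeks and 59% to 67% at 6 weeks. The term removes the bias but does not restore full power when the years are far apart.

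**6. Precision cost.** The standard error of the year effect grows by about √[1 + (d/2)²/4.7²]: 1.022 at 2 weeks, 1.087 at 4 and 1.186 at 6. The simulated values agree: 0.0815 without the term at 0 and 2 weeks; with it, 0.0815 at 0 weeks, 0.0833 at 2, 0.0887 at 4 and 0.0967 at 6.

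**The case against.** Sampling both years in the same February-to-June window, starting in orientation week, is a recognised control for season. Bias needs an imbalance within that window, and no document shows one. Protocol 5.3 ties the council-clinic invitation route to 2018, but protocol 4.1 allows council providers to collect swabs with no year limit, so this establishes no difference in dates. The slope is one serogroup at one UK university, applied to a six-genogroup outcome in school leavers who include people in work. The largest figures need the full slope, no absorption and a 4- to 6-week gap, and an early-concentrated rise roughly halves the false-positive rates. Pub and club visits, kissing, alcohol and current cold or sore throat are adjusted for and are plausible routes for a seasonal or start-of-university effect. The authors had also seen preliminary 2018 data, so leaving timing out may have been deliberate. A sensitivity analysis could be enough.

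Most of this stands, and it is why the point is put as a potential bias with illustrative figures. It does not close the gap. A shared window limits the difference in dates without removing it. The behavioural covariates are mostly yes/no measures of the present, last week or last month, and how much trend they absorb is unknown. If omission was an informed choice, the SAP does not say so. With no timing row, a reader could not check that the years were balanced.

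**Conclusion.** The concern holds. The primary model has no swab-timing term, the by-year table omits timing, and the protocol itself treats within-year change as possible. Should be fixed; confidence medium.

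The size is conditional. If the years share the same swab-date distribution, the bias is zero. At a quarter to half of the assumed slope and a 2-week difference, it is small: false positives of 6% to 8%, or power of 74% to 66% in the masking direction. At 4 weeks it is material: 8% to 15%, or power of 66% to 49%. These figures rest on a borrowed slope, a steady log-odds trend and assumed differences in mean date. The documents supply no local slope and no swab dates. The sample size calculation is not in question.

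**What to change.** - In SAP 6.2, prespecify swab date as a covariate in the adjusted primary model, as month categories or as weeks since the start of the academic year. Either form works: month categories left a residual odds ratio of at most 1.012 in the worst case simulated (6 weeks, full slope), against 1.255 unadjusted.
- In SAP 4.1, add swab month to the by-year table.
- Optionally, add a sensitivity analysis that also includes study status. SAP 4.2 already derives it (for example "Full time study (exclusively TAFE or university student")) and SAP 4.1 already tabulates it by year.

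The cost is SAP wording. Swab date is already needed for SAP 6.1, so no new data are required and the target of 4,096 per year does not change. About 590 carriers are expected (0.08 × 4,096 = 328, plus 0.064 × 4,096 = 262), enough for one to four more terms. The standard error of the year effect is unchanged if dates balance, and rises by about 2%, 9% and 19% at differences of 2, 4 and 6 weeks.
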